# 10.3 Patient Confidentiality

All information obtained during the conduct of the study with respect to the patients' state of health will be regarded as confidential. This is detailed in the written information provided to

the patient. An agreement for disclosure of any such information will be obtained in writing and is included in both copies of the ICF signed by the patient. The study data shall not be disclosed to a third party without the written consent of the sponsor.

#### 10.4 Informed Consent

According to the ICH guideline for GCP (E6), the investigator will obtain and document informed consent for each patient screened for this study. All patients will be informed in writing of the nature of the protocol and investigational therapy, it's possible hazards, and their right to withdraw at any time, and will sign a form indicating their consent to participate prior to the initiation of study procedures. The patient's medical record should contain written documentation indicating that informed consent was obtained. The ICF must be reviewed and approved by the investigator's designated IRB/IEC and by the sponsor. The ICF should include all the elements as outlined in Section 4.8.10 of the ICH guideline for GCP (E6).

#### 10.5 Institutional Review Board

This protocol and relevant supporting data are to be submitted to the appropriate IRB/IEC for review and approval before the study can be initiated. Amendments to the protocol will also be submitted to the IRB/IEC prior to implementation of the change. The sponsor must receive a letter documenting the IRB/IEC approval prior to initiation of the study. The PI is also responsible for informing the IRB/IEC of the progress of the study and for obtaining annual IRB/IEC renewal. The IRB/IEC must be informed at the time of completion of the study and should be provided with a summary of the results of the study by the PI. The PI must notify the IRB/IEC in writing of any SAE or any unexpected AE according to ICH guidelines.

# 11 PROTOCOL MANAGEMENT AND ADMINISTRATIVE CONSIDERATIONS

# 11.1 Study Documentation

The PI and study staff has the responsibility of maintaining a comprehensive and centralized filing system containing all study-related documentation. These files must be available for inspection by the sponsor, representatives of the sponsor, the IRB/IEC, and regulatory authorities (i.e., FDA or international regulatory authorities) at any time, and should consist of the following elements:

Patient files, containing the completed CRFs, supporting source documentation from the medical record including laboratory data and the ICF;

Regulatory files, containing the protocol with all amendments and investigator signature pages, copies of all other regulatory documentation, and all correspondence between the site and the IRB/IEC and sponsor; and Drug accountability files, including a complete account of the receipt and disposition of the study medication (test article).

Records are to be available for 2 years after marketing application approval, or if the application is not approved or never submitted, 2 years after the last shipment and delivery of the material and the appropriate competent regulatory authorities are notified. The sponsor will provide written notification when it is appropriate for the investigator to discard the study-specific documents referenced above.

# 11.2 Protocol Interpretation and Compliance

To ensure accurate interpretation and implementation of the study, the procedures and endpoints defined in the protocol will be carefully reviewed by the PI and his or her staff prior to the time of study initiation. The sponsor and PI will follow all reasonable means to resolve any differences of opinion of matters of eligibility, toxicity and other endpoints. In the event that a resolution cannot be reached then one or both parties may seek to terminate the study following the provisions outlined in the Clinical Trials Agreement.

# 11.3 Study Monitoring

The sponsor or a contracted monitor will visit the study center periodically to monitor adherence to the protocol, compliance with ICH guidelines, adherence to applicable FDA regulations, and the maintenance of adequate and accurate clinical records. Case reports forms will be reviewed to ensure that key safety and efficacy data are collected and recorded as specified by the protocol. The monitor will be permitted to access patients' complete medical records, laboratory data, and other source documentation as needed to monitor the trial appropriately.

# Appendix 1 Guidelines for the Six-minute Walk Test

(Adapted from American Thoracic Society (ATS) Statement: Guidelines for the Six-Minute Walk Test. www.atsjournal.org

#### Location

The 6MWT should be performed indoors preferably, along a long, flat, straight, hallway with a hard surface that is seldom traveled. The walking course must be 15-50 meters in length. Turnaround points should be marked with a brightly colored cone. A starting line, which marks the beginning and end of each lap, should be marked on the floor with brightly colored tape. If possible, the subject should use the same 6MWT location for each test and same pair of shoes.

#### **Safety Issues**

- 1. Testing should be performed in a location where a rapid, appropriate response to an emergency is possible. The appropriate location of a crash cart should be determined by the physician supervising the facility.
- 2. Supplies that should be available include oxygen, sublingual nitroglycerine, aspirin, and albuterol (eg, a beta agonist by metered dose inhaler or nebulizer). A telephone or other means should be in place to enable a call for help.
- 3. The technician should be certified in cardiopulmonary resuscitation with a minimum of Basic Life Support and American Health Association-approved cardiopulmonary resuscitation course (or equivalent). Advanced cardiac life support certification is desirable. Training, experience, and certification in related health care fields (registered nurse, registered respiratory therapist, certified pulmonary function technician, etc) are also desirable. A certified individual should be readily available to respond if needed.
- 4. Physicians are not required to be present during all tests. The physician ordering the test or supervising a laboratory physician may decide whether physician attendance at a specific test is required.

Reasons for immediately stopping a 6MWT include the following: (1) chest pain, (2) intolerable dyspnea, (3) leg cramps, (4) staggering, (5) diaphoresis, and (6) pale or ashen appearance.

Technicians must be trained to recognize these problems and the appropriate responses. If a test is stopped for any of these reasons, the subject should sit or lie supine as appropriate depending on the severity or the event and the technician's assessment of the severity of the event and the risk of syncope.

#### **Equipment in the Vicinity**

- 1.  $O_2$  saturation equipment + forehead probes.
- 2. Countdown timer or stopwatch.
- 3. Mechanical lap counter.

- 4. Two small cones to mark the turnaround points.
- 5. A chair that can be easily moved along the walking course.
- 6. Worksheets.
- 7. A source of oxygen.
- 8. Telephone.
- 9. Automated electronic defibrillator.

## **Subject Preparation**

- 1. Comfortable clothing should be worn.
- 2. Appropriate shoes for walking should be worn preferably the same pair for each test.
- 3. A subject should use his or her usual walking aids during the test (cane, walker, etc).
- 4. The subject's usual medical regimen should be continued and study drug taken in the morning before the commencement of the 6MWT.
- 5. A light meal is acceptable before early morning or early afternoon tests.
- 6. Subjects should not have exercised vigorously within 2 hours of beginning the test.

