Study drug administration v		X	X	X	X	X	X	X	X	X	X
Pharmacokinetic blood sample w		X	X	X	X	X	X	X	X	X	X
Adverse event monitoring	•	-	•	-	•	•	•	-	•	•	→
Concomitant medication monitoring	←										→

Optional blood sample (4mL) for DNA testing, to be taken pre-dose on Day 1.

<sup>m Serum hCG pregnancy test required at Screening and at Week 5; urine pregnancy test at Day1.

<sup>n Blood sample for BNP/NT-proBNP to be taken after 1-hour rest and prior to administration of 6MWT.

<sup>o 6MWT should be completed pre-dose at approximately the same time of day at each designated visit.

Two 6MWTs are required during Screening and each test must be performed on a separate day. The distance walked during each test must be ≥100 meters and ≤500 meters, and within 15% of each other in order to be eligible for the study.

Thromboembolic disease assessment to include a V/Q scan or spiral/helical/electron beam computed tomography utilizing an angiography protocol, or selective pulmonary angiogram, unless performed within 5 years prior to Screening.

Pulmonary function test (PFT) to be completed at screening. A PFT completed within 6 months prior to Screening may be acceptable (see inclusion criteria #9).

s See exclusion criteria #10

t Transthoracic or transesophageal ECHO, unless performed within 12 months prior to Screening.

<sup>u A Baseline RHC is required. Patients who have had a RHC performed within 30 days of screening and meet study entry requirements are not required to have a repeat screening RHC.

V Should be taken with food.

Blood samples for PK will be collected at pre-dose and at 4 hours post-dose during every visit in which dose escalation occurs and one week after the last dose escalation. An additional blood sample for PK analysis will be collected if possible at the time of any intolerable AE or SAE.

Table 2. Schedule of Procedures and Visits: Treatment and Dose Transition Periods

			Transition Period				
Evaluation a		Treatment Period	End of Study (EOS) Visit	Follow-up Visit (start of OLE) ±1 week b			
Study Week	10	14	18	22°	25		
Day	70	98	126	154	175		
Physical exam				X	X		
Safety ECG (12-lead) d	X	X	X	X	X		
Clinical laboratory tests e	X	X	X	X	X		
Serum pregnancy test f	X	X	X	X	X		
Vital signs g	X	X	X	X	X		

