Study drug administration h,i	→ j						
Six-minute walk test k	X	X	X	X	X		
Right heart catheterization				X l			

<sup>a Reference to pre-dose and post-dose activities in this schedule apply to the morning dose of study drug.

For patients who terminate early from the study and is unable to return for the follow-up visit at Week 25, AE and concomitant medication follow-up may be conducted by telephone.

<sup>c Patients should have all assessments including RHC, 6MWT and BNP/NT-proBNP completed prior to entering the transition period.

d Safety ECGs should be completed **pre-dose**.

<sup>e Clinical laboratory tests will include hematology, serum chemistry, coagulation, and urinalysis. Clinical laboratory tests will be completed **pre-dose**.

Serum pregnancy test will be completed **pre-dose** at each visit during the treatment period.

Vital sign measurements (blood pressure, heart rate, respirations, body temperature, and pulse oximetry, taken in supine position after 5-minute rest) will be taken **pre-dose**.

<sup>h Study drug should be taken with food.

On days with scheduled study visits, patients should **not** take their morning dose of study medication at home in order to complete pre-dose study procedures.

Patients entering the APD811-007 study will remain on current dose through the transition period. Patients who do not continue into the APD811-007 study will discontinue study medication at Week 22 visit but not prior to undergoing the final RHC, and will return for follow-up visit at Week 25; if the patient is unable return for the follow-up visit, AE and concomitant medication follow-up may be conducted by telephone.

<sup>k 6MWT should be completed **pre-dose** at approximately the same time of day at each designated visit.

			Transition Period			
Evaluation a		Treatment Period	End of Study (EOS) Visit	Follow-up Visit (start of OLE) ±1 week b		
Study Week	10	14	18	22 c	25	
Day	70	98	126	154	175	
BNP/NT-proBNP m	X			X	X	
Pharmacokinetic blood sample n	X	X	X	X		
WHO/NYHA functional class assessment o	X	X	X	X	X	
Assessment of clinical worsening	X	X	X	X	X	
Adverse event monitoring	+					
Concomitant medication monitoring	+				—	

RHC will be performed as part of Week 22 end-of-study procedures.

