#### 6.6 Six-minute Walk Test

The 6MWT will be conducted the according to the modified guidelines issued by the American Thoracic Society, "ATS Statement: Guidelines for the Six-minute Walk Test". Technicians performing the test will be trained according to published procedures (Appendix 1). Tests will be performed at approximately the same time of day for each test in order to minimize intraday variability.

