# 7.3 Study Procedures

# 7.3.1 Study Procedures for Dose Titration Period

Patients who meet all the entry criteria and are eligible for the study will report to the clinical study unit to confirm eligibility for the study and complete all Day 1 baseline procedures and receive study medication and instructions. The study medication will be given in the morning at the study site on Day 1. The patient should be observed for at least 4 hours after the dose.

Clinic visits will occur for each escalation of study drug dose. Visits should be entered based on the study week as noted in Table 1. There should be at least one study visit each week during the dose titration period. Beyond this visit, any additional visit during the dose titration period will be documented as an 'unscheduled' visit.

If a patient reaches the highest dose tolerated prior to Week 9, and no additional dose escalations are planned, the visit schedule may be amended at the investigator's discretion. However, visits at Weeks 1, 2, 5, and 9 of the dose titration period are mandatory.

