# 7.4 Baseline/Day 1 Visit (Week 1)

Once Screening and Baseline procedures are completed, and the patients' urine pregnancy test (if applicable) has been confirmed as negative, the patient will be given the first dose of study drug (Day 1). Study drug should be given with food. The date of initial drug administration is Day 1 and must be on the same day that the Baseline evaluations are performed.

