#### 7.4.1 Pre-dose Procedures for Dose Titration Visits

- Vital signs pre-dose according to Table 1
- Safety ECG pre-dose on Day 1 and Weeks 1- 9 according to Table 1
- WHO/NYHA functional class assessment
- Assessment of clinical worsening
- Clinical laboratory tests (to include hematology, coagulation parameters [PT/PTT, INR], serum chemistry, and urinalysis) according to Table 1
- Optional blood sample for DNA testing according to Table 1
- Pregnancy test according to Table 1
- BNP/NT-proPNP: blood sample to be taken after 1-hour rest and prior to administration of 6MWT according to Table 1
- 6MWT according to Table 1
- PK blood draw: pre-dose according to Table 1
- Record adverse events
- Record concomitant medications

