1.2.2 Efficacy Assessments

1.2.2.1 Six Minute Walk Test (6MWT)

The 6MWT will be conducted according to the modified guidelines issued by the American Thoracic Society, “ATS Statement: Guidelines for the Six-minute Walk Test”. Technicians performing the test will be trained according to published procedures. Tests will be performed at approximately the same time of day for each test in order to minimize intraday variability. The 6MW distance will be analyzed at Day 1 prior to study drug administration, and at, Weeks 5, 10, 14, 18 and 22.

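### Protocol Appendix 1 has study drug taken before the six-minute walk, while the visit schedules put the walk before the morning dose

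*Protocol*

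**What the plan says.** **Drug before walk.** Protocol Appendix 1, Subject Preparation, item 4 asks that the usual regimen be continued and "study drug taken in the morning before the commencement of the 6MWT". Protocol Section 6.6 names Appendix 1 as the procedure for technician training.

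**Walk before drug.**
- Protocol Table 1, footnote o (screening, Day 1, Week 5): "6MWT should be completed pre-dose at approximately the same time of day at each designated visit". Table 2, footnote k, repeats this for Weeks 10 to 25.
- Protocol Table 2, footnote i: on visit days patients should not "take their morning dose of study medication at home in order to complete pre-dose study procedures".
- Protocol Section 7.4.1, headed "Pre-dose Procedures for Dose Titration Visits", includes the 6MWT in its list.
- SAP Appendix 2, footnotes i and k of the treatment-period schedule, match Table 2.

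Footnote a of each schedule ties pre-dose and post-dose to the morning dose of study drug.

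**Day 1.** Protocol Section 7.3.1: "The study medication will be given in the morning at the study site on Day 1". Section 7.4 gives the first dose "Once Screening and Baseline procedures are completed". SAP Section 1.2.2.1: "The 6MW distance will be analyzed at Day 1 prior to study drug administration".

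**The concern.** Both instructions are current text and cannot both be followed on the same visit morning. I found no statement of which prevails, and the wrong one sits in the document used by the people who run the test.

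Change from baseline in 6MWD at Week 22 is the second of two primary endpoints, tested only if PVR is significant. If some sites walk patients before the dose and others after it, on-treatment distances are taken at different points of the dosing interval. For a drug that affects walking, this could move the APD811-placebo difference and add variation between sites. A mistimed Week 5 walk would enter the primary 6MWD analysis only where LOCF carries it forward.

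**Working it through.** **1. Can the two texts be reconciled?** No. Footnote a means that pre-dose cannot be read as before the evening dose. The schedules agree with each other, with Section 7.4.1 and with the SAP. Item 4 stands alone, so it is the error.

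**2. Which visits are exposed?**

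| Visit | What protects the walk | What remains open |
|---|---|---|
| Day 1 | Sections 7.3.1, 7.4, 7.4.1; SAP 1.2.2.1 | Nothing material |
| Week 5 | Table 1 footnote o; Section 7.4.1; laboratory tests, functional class and first ECG also pre-dose | A clinic dose after those procedures and before the walk |
| Weeks 10-22 | Table 2 footnotes i and k; laboratory tests, ECG, vital signs, functional class and first PK sample also pre-dose | The same. Section 7.4.3 lists the 6MWT without dose timing, and Section 6.8 recommends the Week 22 catheterization about 4 h after a dose |

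**3. The plan's 6MWD power.** Inputs (Protocol 9.3, SAP 7.1): 40 vs 20 patients, difference 50 m, SD 65 m. I use two-sided 0.05.
- Standard error = 65 × √(1/40 + 1/20) = 17.80 m; 50/17.80 = 2.809.
- Normal approximation: Φ(2.809 − 1.960) = 80.2%. Noncentral t, 58 df: 78.9%.

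The stated 80% reproduces.

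**4. Pre-dose versus 4 h contrast.** Inputs (Protocol 1.1.3): half-life 20.5 to 26.4 h, fed tmax about 4 h. Dosing is b.i.d., so the pre-dose point is taken as 12 h. Assumptions: mono-exponential decline from 4 h to 12 h, and effect on walking proportional to concentration.
- Fall over 8 h = 1 − exp(−ln2 × 8/t½): 23.7% at 20.5 h and 18.9% at 26.4 h.
- If 50 m is the effect at 4 h, the contrast d = 50 × fall: 9.5 to 11.8 m.
- If 50 m is the pre-dose effect, d = 50 × (exp(ln2 × 8/t½) − 1): 11.7 m at 26.4 h and 15.5 m at 20.5 h.

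**5. Shift in the treatment difference.** Let f be the share of APD811 patients whose analysed walk was post-dose. The shift is f × d. The documents give no value for f, so I show it per 10%:
- 0.10 × 9.5 = 0.95 m and 0.10 × 15.5 = 1.55 m, or 1.9% to 3.1% of 50 m.
- If APD811 has no effect on walking, d = 0 and so is the shift.

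**6. Noise only.** Mixed timing raises the APD811-arm SD to √(65² + f(1 − f)d²), which is largest at f = 0.5.
- With d = 15.5: √(4225 + 0.25 × 240.25) = 65.46 m.
- Pooled with SD 65 in the placebo arm: √((39 × 65.46² + 19 × 65²)/58) = 65.31 m. Power is 78.5%.
- With the extra variance kept in the APD811 arm only, power is 78.7%.

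The loss from 78.9% is at most 0.4 points.

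**The case against.** The best defence is that item 4 is one clause against explicit timing rules in both schedules, and that visit routine would override it. Pre-dose tests at Week 5 and at Weeks 10 to 22 mean that a patient who dosed at home could not comply with the visit. Walks are held at about the same time of day, and Appendix 1 already records the time of the test. PK samples before and 4 h after dosing at the treatment-period visits in practice require a known dose time (my inference), so mistimed walks could probably be found afterwards. All of this stands as a reason to expect few post-dose walks. None of it prevents a dose in clinic between the other pre-dose procedures and the walk, which is the order that item 4 prescribes.

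The metre figures also deserve caution. The documents give no concentration-effect relation for walking, and the PK comes from phase 1. The calculation shows a larger APD811 effect post-dose only because proportionality is assumed; the documents do not settle the sign.

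A reader might infer more than the documents support:
- **A contaminated baseline.** The Day 1 walk is placed before the first dose in several places.
- **Week 5 as an unprotected visit.** It has its own pre-dose procedures, as the later visits do.
- **A route to a false positive on 6MWD.** Dose timing creates no difference if the drug has no effect on walking.
- **Damage to the PVR result.** Measured PVR is untouched. Last on-treatment 6MWD is one of several predictors in the imputation model for missing PVR (SAP 7.4), but the documents give nothing from which to size that path.

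**Conclusion.** The contradiction is real, and item 4 is wrong as written. It is more than clerical, because it would change when a primary endpoint is measured at any site that trains to it. The severity is minor. On the proportional-effect assumption and the documents' phase 1 PK, the contrast is about 9 to 16 m on a 50 m effect, and the treatment difference moves roughly 1 to 1.6 m per 10% of APD811 patients walked post-dose. The power loss from noise is under one point. The true size is unknown, because the documents give neither an acute effect of APD811 on walking nor the share of walks that would be mistimed. The sample size and the analysis model need no change.

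**What to change.** Reword Appendix 1, Subject Preparation, item 4 to say that usual background medication is continued and that the morning dose of study drug is held until after the 6MWT at every visit. This costs one sentence in a protocol amendment or a memo to sites. Recording the time of the last study drug dose beside the walk time is optional: it adds one field to the worksheet, and the PK sampling records may already supply the information.

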#### Measurements

- 1. Repeat testing should be performed about the same time of day to minimize intra-day variability.
- 2. A "warm-up" period before the test should not be performed.
- 3. The subject should sit at rest in a chair, located near the starting position, for at least 10 minutes before the test starts. During this time, check for contraindications and make sure that clothing and shoes are appropriate. Record all pertinent information surrounding the test (ie, starting location, length of hallway, direction the subject will be walking, time of test, subject's general condition/feeling on the day of the test, and any other physical or medical information that may potentially influence the results of the test).
- 4. Subjects who require supplemental oxygen must breathe a stable oxygen dose for at least 15 minutes prior to the measurement of SpO2 and until the end of the 6MWT (see below for SpO2 requirements). It is critical that if oxygen was utilized during the Screening 6MWTs, that it be utilized during all subsequent on-study tests and that it is delivered in the same manner with the same flow. Note whether the oximeter signal quality is acceptable.
- 5. Set the lap counter to 0 and the time to 6 minutes. Assemble all necessary equipment (lap counter, timer, worksheets, etc.) and move to the starting point.
- 6. Instruct the subject as follows:

The object of this test is to walk as far as possible for 6 minutes. You will walk back and forth in this hallway. Six minutes is a long time to walk, so you will be exerting yourself. You will probably get out of breath or become exhausted. You are permitted to slow

down, to stop, and to rest as necessary. You may lean against the wall while resting, but resume walking as soon as you are able.

You will be walking back and forth around the cones. You should pivot briskly around the cones and continue back the other way without hesitation. Now I'm going to show you. Please watch the way I turn without hesitation.

Demonstrate by walking one lap yourself. Walk and pivot around a cone briskly.

Are you ready to do that? I am going to use this counter to keep track of the number of laps you complete. I will click it each time you turn around at this starting line. Remember that the object is to walk AS FAR AS POSSIBLE for 6 minutes, but don't run or jog.

Start now or whenever you are ready.

- 7. Position the subject at the starting line. You should also stand near the starting line during the test. Do not walk with the subject. As soon as the subject starts to walk, start the timer
- 8. Do not talk to anyone during the walk. Use an even tone of voice when using the standard phrases of encouragement. Watch the subject. Do not get distracted and lose count of the laps. Each time the participant returns to the starting line, click the lap counter once (or mark the lap on the worksheet). Let the participant see you do it. Exaggerate the click using body language, like using a stopwatch at a race.

After the first minute, tell the subject the following (in even tones): *You are doing well. You have 5 minutes to go.* 

When the timer shows 4 minutes remaining, tell the subject the following: *Keep up the good work. You have 4 minutes to go.* 

When the timer shows 3 minutes remaining, tell the subject the following: *You are doing well. You are halfway done.* 

When the timer shows 2 minutes remaining, tell the subject the following: *Keep up the good work. You have only 2 minutes left.* 

When the timer shows 1 minute remaining, tell the subject: You are doing well. You have only 1 minute to go.

Do not use other words of encouragement (or body language) to speed the subject up.

If the subject stops walking during the test and needs a rest, say this: You can lean against the wall if you would like: then continue walking whenever you feel able. Do not stop the timer. If the subject stops before the 6 minutes are up and refuses to continue (or you decide that they should not continue), wheel the chair over for the subject to sit on, discontinue the walk and note on the worksheet the distance, the time stopped, and the reason for stopping prematurely.

When the timer is 15 seconds from completion, say this: *In a moment I'm going to tell you to stop. When I do, just stop right where you are and I will come to you.* 

When the time rings (or buzzes), say this: *Stop!* Walk over to the subject. Consider taking the chair if they look exhausted. Mark the spot where they stopped by placing a bean bag or a piece of tape on the floor.

- 9. Record the number of laps from the counter (or tick marks on the worksheet).
- 10. Record the additional distance covered (the number of meters in the final partial lap) using the markers on the wall as distance guides (or use a tape measure). Calculate the total distance walked, rounding to the nearest meter, and record it on the worksheet.
- 11. Congratulate the subject on good effort and offer a drink of water.

